1.2 Study design

This is a multicenter, prospective open-labeled phase Ib trial based on a dose escalation study design (3+3 traditional design) assessing three dose levels of trabectedin given in combination with durvalumab, followed by two expansion cohorts (STS and ovarian carcinomas) once the MTD has been established.

2 Definition of the study population

2.1 Definitions

2.1.1 Dose escalation part

The following patients will not be included in the population assessable for safety (primary analysis) and thus will be replaced:

- Patients who received $\leq 75\%$ RDI (Relative Dose Intensity) for trabectedin OR $\leq 75\%$ RDI for durvalumab over cycle 1, due to drug-related AE not considered as DLT.
- Patients who goes off treatment over cycle 1 for reasons unrelated to toxicity (DLT or any other AE), e.g. progression, lost to follow-up, will be replaced Population assessable for safety (primary analysis); all patients who completed the DLT assessment period or who developed DLT are included in the analysis.

2.1.2 Expansion cohorts

- Eligible population: All patients included without major violation of eligibility criteria.
- Population assessable for efficacy: All patients eligible and for whom the following conditions are statisfied:
 - Received at least one complete or two incomplete treatment cycles,

- At least one disease measurement recorded not less than six weeks after treatment onset.
- The following patients will also be included in the population assessable for efficacy; they will be considered as “inevaluable for response” for the primary endpoint as per RECIST v1.1 criteria (i.e. objective response under treatment) and not be replaced in the primary efficacy analysis:
 - Any eligible patients who received at least one treatment cycle or two incomplete treatment cycles and experience disease progression or die due to disease progression prior to response evaluation (will be considered as “inevaluable for response” due to early, progression).
 - Patients withdrawn due to drug-related toxicity without any tumor assessments after the start of study treatment (will be considered as “inevaluable for response” due to toxicity).
 - Patients who received at least one administration of the treatment AND withdrawn due to significant clinical deterioration of unknown reason AND without any tumor assessments after the start of study treatment (will be considered as “inevaluable for response” due to significant clinical deterioration).
- Safety population: all patients having received at least one (any) treatment administration.

Patient's replacement:

- Any patient not eligible or not assessable for efficacy will be replaced.
- However, any patient who received at least one administration of the study drug will be included in the safety analysis.

2.2 Eligibility status

2.2.1 Screening failure

Inclusion and non-inclusion criteria will not be verified for the screen failures (variable SCR_PT=1).

2.2.2 Inclusion criteria

Criteria	eFORM Variable	Control WHERE SCR_PT=0 (Screening failures exclusion)
1. Histology : - Soft-tissue sarcoma histologically confirmed. In care outside a center of the RRePS Network, a central review is necessary ([name] team), - histologically confirmed ovarian carcinoma (carcinosarcoma included), without known g/s BRCA mutation	INCLUSION CRITERIA C1I DISEASE HISTORY HIST_REV DIAGNOSIS OVARIAN STS	OK if: (C1I = 1 and (HIST_REV = 1 and DIAGNOSIS= 1 and STS=1) or (C1I = 1 and HIST_REV = 1 and DIAGNOSIS= 2 and OVARIAN=0)
2. ovarian carcinoma must have received atleast one line of platinum-containing regimen.	INCLUSION CRITERIA C2I DISEASE HISTORY DIAGNOSIS PREVIOUS TREATMENT OF THE TUMOR CHEMOTH PLATINIUM	OK if: C2I = 1 and (CHEMOTH =1 and PLATINIUM =1 where DIAGNOSIS = 2)
3. Metastatic or unresectable locally advanced disease, not ammenable to curative therapy,	INCLUSION CRITERIA C3I DISEASE STATUS AT INCLUSION LA_DIS META_DIS	OK if: C3I = 1 and (LA_DIS = 1 or META_DIS = 1)
4. Age \geq 18 years,	INCLUSION CRITERIA C4I ASSESSMENT OF INCLUSION DT_BIRTH DT_CONS DT_INC	OK if: C4I = 1 and D_BIRTH GE 18 Where D_BIRTH is a new variable : Format DT_BIRTHBIS ddmmyy10.; DT_BIRTHBIS =MDY(substr(DT_BIRTH,1,2), 15, substr(DT_BIRTH,4,4)); D_BIRTH=round((DT_INC- DT_BIRTHBIS)/365.25,0.1); Label D_BIRTH ='DELAY'
5. Eastern Cooperative Oncology	INCLUSION CRITERIA	OK if: C5I = 1 and

Group (ECOG) performance status (PS) ≤ 1,	C5I BASELINE CONDITION AND M. HIST. ECOG_PTR C1D1-CLINICAL EXAMINATION ECOG_CYC DT_VISIT C1D1-D2 TREATMENT DT_TRA (Trabectedin administration date)	ECOG_PTR in (0 1) OR IF C5I = 1 and (ECOG_PTR in (-2 -9)) and (ECOG_CYC in (0 1)) and ((DT_TRA - DT_VISIT) > 0)
6. Life expectancy > 3 months,	INCLUSION CRITERIA C6I	OK if: C6I = 1 Investigator decision
7. Patients must have measurable disease (lesion in previously irradiated field can be considered as measurable if progressive at inclusion according to RECIST v1.1) defined as per RECIST v1.1 with at least one lesion that can be measured in at least one dimension (longest diameter to be recorded) as ≥ 10 mm with spiral CT scan,	INCLUSION CRITERIA C7I TUMOR ASSESSMENT BASELINE NUM_LESI MEA1INC – MEA5INC	OK if: C7I = 1 and NUM_LESI GT 0 and ((MEA1INC or MEA2INC or MEA3INC or MEA4INC or MEA5INC) GE 10)
8. Documented disease progression according to RECIST v1.1 before study entry,	INCLUSION CRITERIA C8I DISEASE STATUS AT INCLUSION DT_LPROG	OK if: C8I = 1 and DT_LPROG completed
9. Patient must comply with the collection of tumor biopsies,	INCLUSION CRITERIA C9I ASSESSMENT OF INCLUSION DT_INC BIOPSY BIOPS C1D1 - BIOPSY BIOP_PHAR C1D1-CLINICAL EXAMINATION DT_VISIT	OK if: C9I = 1 and ((BIOPS=1) or (BIOPS=2 and BIOP_PHAR=1 and (DT_VISIT - DT_INC LE 0)))
10. At least 1 line of chemotherapy in the palliative setting with use of Anthracyclines (for STS),	INCLUSION CRITERIA C10I DISEASE HISTORY DIAGNOSIS PREVIOUS TREATMENT OF THE TUMOR CHEMOTH ANTHRA	For STS (DIAGNOSIS= 1) , OK if: C10I = 1 and CHEMOTH = 1 and ANTHRA =1
11. At least three weeks since	INCLUSION CRITERIA	Find the last treatment:

last chemotherapy, immunotherapy or any other pharmacological treatment and/or radiotherapy,
	
C11I ASSESSMENT OF INCLUSION DT_INC DISEASE HISTORY CHEMOTH (chemotherapy) T_CHEIMM (targeted chemo /immunotherapy) DT_CHEME (date of last line of chemo) RADIO (radiotherapy) DT_LSEQ (last sequence)
	
For radiotherapy (RADIO=1): If (RADIO=1) then DT_LTTRT=DT_LSEQ
 
For chemotherapy (CHEMTH=1)/targeted chemotherapy/immunotherapy (T_CHEIMN): If (CHEMOTH =1 or T_CHEIMM=1) then Do ; DT_LTTRT=DT_CHEME End;
 
OK If : C7I = 1 and (DT_INC– DL_LTTRT GE 21 days)


12. Adequate hematological, renal, metabolic and hepatic function:
 
a. Hemoglobin \geq 9 g/dl (patients may have received prior red blood cell [RBC] transfusion, if clinically indicated); absolute neutrophil count (ANC) \geq 1.5 $\times 10^9/l$, and platelet count \geq 100 $\times 10^9/l$.
 
b. Alanine aminotransferase (ALT), aspartate aminotransferase (AST) \leq 2.5 \times upper limit of normality (ULN) and alkaline phosphatase (AP) \leq 2.5 \times ULN.
 
c. Total bilirubin \leq ULN.
 
d. Albumin \geq 25 g/l.
 
e. Calculated creatinine clearance (CrCl) $>$ 60 ml/min (according to Cockcroft Gault formula).
 
f. Thyroid function within normal laboratory ranges (TSH, free T3, free T4)
 
g. Creatine PhosphoKinase (CPK) \leq 2.5 \times ULN
	
INCLUSION CRITERIA C12I LABORATORY TEST
 
HEMO NEUT PLAT ALT AST ALKA BILI ALBU CREAC TSH FREE T3 FREE T4 CPK
	
C12I = 1 and HEMO GE 9 and NEUT GE 1.5 and PLAT GE 100 and ALBU GE 25 and CREAC GT 60 and AST completed and ALT completed and ALKA completed and BILI completed and TSH completed and T3 completed and T4 completed and CPK completed
 
Investigator decision for the value of the following laboratory tests: ASAT/ALAT/Alka/Total Bilirubin/TSH/free T3/free T4/CPK
 
$10^9/l = G/L$

13. Women of childbearing potential must have a negative serum pregnancy test within 72 hours prior to receiving the first dose of trial medication. Both women and men must agree to use a
	
INCLUSION CRITERIA C13I ASSESSMENT OF INCLUSION SEX REPROD BASELINE COND. AND M. HIST.
	
OK if: C13I=1 AND ((SEX=2 and REPROD=2) or (SEX=2 and REPROD=1 and PREG_PTR = 1 and DT_PREG completed and R_PREG = 0 and DT_TRA - DT_PREG>=0 and DT_TRA -

highly effective method of contraception throughout the treatment period and for six months after discontinuation of treatment. Acceptable methods of contraception are described in protocol section 7.6.1.1,	PREG_PTR DT_PREG R_PREG CONT_PTR C1D1 DT_TRA	DT_PREG<=3 and CONT_PR=1) OR (SEX=1 and CONT_PR=1)
14. No prior or concurrent malignant disease diagnosed or treated in the last 2 years except for adequately treated in situ carcinoma of the cervix, basal or squamous skin cell carcinoma, or in situ transitional bladder cell carcinoma,	INCLUSION CRITERIA C14I	C14I = 1 Investigator decision
15. Recovery to grade \leq 1 from any adverse event (AE) derived from previous treatment (excluding alopecia of any grade and non-painful peripheral neuropathy grade \leq 2) according to the National Cancer Institute Common Terminology Criteria for Adverse Events (NCI-CTCAE, version 4.03),	INCLUSION CRITERIA C15I	C15I = 1 Investigator decision
16. Voluntarily signed and dated written informed consent prior to any study specific procedure,	INCLUSION CRITERIA C16I ASSESSMENT OF INCLUSION DT_CONS	C16I = 1 and DT_CONS completed (or filled)
17. Patients with a social security in compliance with the French law relating to biomedical research (Article 1121-11 of French Public Health Code).	INCLUSION CRITERIA C17I	C17I = 1 Investigator decision

2.2.3 Non-inclusion criteria

Criteria	eFORM Variable	Control
		WHERE SCR_PT=0 (Screen failures exclusion)
1. Previous treatment with Trabectedin or an anti-PD-1, anti-PD-L1, anti-PD-L2, including Durvalumab,	ELIGIBILITY FORM C1NI	C1NI = 0 Investigator decision
2. Current or prior use of immunosuppressive medication including any use of oral glucocorticoids, within 21 days before the first dose of	ELIGIBILITY FORM C2NI	C2NI = 0 Investigator decision

durvalumab, with the exceptions of intranasal and inhaled corticosteroids or systemic corticosteroids at physiological doses		
3. Active or prior documented inflammatory bowel disease (e.g., Crohn's disease, ulcerative colitis),	ELIGIBILITY FORM C3NI	C3NI = 0 Investigator decision
4. Has an active autoimmune disease requiring systemic treatment within the past 2 years (ie, with use of disease modifying agents, corticosteroids or immunosuppressive drugs). Replacement therapy (e.g., thyroxine, insulin, or physiologic corticosteroid replacement therapy for adrenal or pituitary insufficiency) is not considered a form of systemic treatment,	ELIGIBILITY FORM C4NI	C4NI = 0 Investigator decision
5. Has evidence of active non-infectious pneumonitis,	ELIGIBILITY FORM C5NI	C5NI = 0 Investigator decision
6. Has an active infection requiring systemic therapy,	ELIGIBILITY FORM C6NI	C6NI = 0 Investigator decision
7. Currently active bacterial or fungus infection (> grade 2 NCI-CTCAE] HIV1, HIV2, hepatitis A or hepatitis B or hepatitis C infections),	ELIGIBILITY FORM C7NI LABORATORY TEST HEP_A HEP_B HEP_C HIV	C7NI = 0 and HEP_A NE 1 and HEP_B NE 1 and HEP_C NE 1 and HIV NE 1 Investigator decision
8. Known central nervous system malignancy (CNS),	ELIGIBILITY FORM C8NI	C8NI = 0 Investigator decision
9. Men or women of childbearing potential who are not using an effective method of contraception as previously described; women who are pregnant or breast feeding,	ELIGIBILITY FORM C9NI ASSESSMENT OF INCLUSION SEX REPROD BASLINE COND. AND M. HIST. PREG_PTR DT_PREG R_PREG CONT_PTR	C9NI = 0 and $((SEX=2 \text{ and } REPROD=2) \text{ OR } (SEX=2 \text{ and } REPROD=1 \text{ and } PREG_PTR = 1 \text{ and } DT_PREG \text{ completed and } R_PREG = 0 \text{ and } CONT_PR=1) \text{ OR } (SEX=1 \text{ and } CONT_PR=1))$ Investigator decision
10. Previous enrolment in the present study,	ELIGIBILITY FORM C10NI	C10NI = 0 Investigator decision

11. Patient unable to follow and comply with the study procedures because of any geographical, social or psychological reasons,	ELIGIBILITY FORM C11NI	C11NI = 0 Investigator decision
12. Has received a live vaccine within 30 days prior to the first dose of trial treatment, Note: the killed virus vaccines used for seasonal influenza vaccines for injection are allowed; however intranasal influenza vaccines (e.g., FluMist®) are live attenuated vaccines and are not allowed.	ELIGIBILITY FORM C12NI	C12NI = 0 Investigator decision
13. Known hypersensitivity to any involved study drug or any of its formulation components,	ELIGIBILITY FORM C13NI	C13NI = 0 Investigator decision
14. Tumors not accessible for biopsy,	ELIGIBILITY FORM C14NI BIOPSY BIOPS ASSESSMENT OF INCLUSION DT_INC C1D1 - BIOPSY BIOP_PHAR DT_BIOPH C1D1-CLINICAL EXAMINATION DT_VISIT	C14NI = 0 and BIOPS = 1 or (BIOPS=2 and BIOP_PHAR=1 and (DT_BIOPH - DT_INC > 0)) Investigator decision
15. Known history of active tuberculosis,	ELIGIBILITY FORM C15NI	C15NI = 0 Investigator decision
16. Person under judicial protection or deprived of liberty.	ELIGIBILITY FORM C16NI	C16NI = 0 Investigator decision
17. Cardiac dysfunction : - LVEF (Left Ventricular Ejection Fraction)< 40% at baseline; - or clinically symptomatic cardiac dysfunction (any % of LVEF at baseline),	ELIGIBILITY FORM C17NI BASELINE COND. AND M. HIST. LVEF	C17NI = 0 and LVEF >=40 Investigator decision
18. Concomitant use of strong inhibitors or inductors of cytochrome CYP3A4 taken within 21 days prior to the first dose of study drug	ELIGIBILITY FORM C18NI	C18NI = 0 Investigator decision

2.2.4 Eligible population

- Eligible population: All patients included without major violation of eligibility criteria.

Criteria	eFORM variable	Program (SAS)
Eligible Population	ELIGIBILITY FORM C1I C2I C3I C4I C5I C6I C7I C8I C9I C10I C11I C12I C13I C14I C15I C16I C17I C1NI C2NI C3NI C4NI C5NI C6NI C7NI C8NI C9NI C10NI C11NI C12NI C13NI C14NI C15NI C16NI C17NI	ELI=1 If (C1I = 0 or C2I = 0 or C3I = 0 or C4I = 0 or C5I = 0 or C6I = 0 or C7I = 0 or C8I = 0 or C9I = 0 or C10I = 0 or C11I = 0 or C12I = 0 or C13I = 0 or C14I = 0 or C15I = 0 or C16I = 0 or C17I = 0 or C1NI = 1 or C2NI = 1 or C3NI = 1 or C4NI = 1 or C5NI = 1 or C6NI = 1 or C7NI = 1 or C8NI = 1 or C9NI = 1 or C10NI = 1 or C11NI = 1 or C12NI = 1 or C13NI = 1 or C14NI = 1 or C15NI = 1 or C16NI = 1 or C17NI = 1) then ELI=0

CREATION OF A NEW INDICATOR VARIABLE

Patients fulfilling inclusion and non-inclusion criteria will be considered as **ELIGIBLE (ELI=1)**.

New binary variable ELI

Label: « Eligibility based on CRF»

ELI=1 if the patient is eligible

ELI=0 if the patient is not eligible

2.3 Dose escalation part/ Assessable for safety

The following patients will not be included in the population assessable for safety (primary analysis) and thus will be replaced:

- Patients who received $\leq 75\%$ RDI (Relative Dose Intensity) for trabectedin OR $\leq 75\%$ RDI for durvalumab over cycle 1, due to drug-related AE not considered as DLT.
- Patients who goes off treatment over cycle 1 for reasons unrelated to toxicity (DLT or any other AE), e.g. progression, lost to follow-up, will be replaced.

Population assessable for safety (primary analysis): all patients who completed the DLT assessment period or who developed DLT are included in the analysis.

CREATION OF A NEW INDICATOR VARIABLE

New binary variable TOL

Label: « Assessable for Safety»

TOL = 1 if the patient is assessable for safety (primary analysis)

TOL = 0 if the patient is not assessable for safety (primary analysis)

Criteria	eFORM variable	Control / program
Patient received $\leq 75\%$ RDI (Relative Dose Intensity) for trabectedin OR $\leq 75\%$ RDI for durvalumab over cycle 1, due to drug-related AE not considered as DLT	CYCLE 1 – DAY 1 AND DAY 2 (WEEK1) TREATMENT Trabectedin DOSE_TRA (dose) VPRE_TRA (volume of preparation) VOL_TRA (administered volume) WHY_TRA (2=AE related to treatment) Durvalumab DOSE_DU VPRE_DU VOL_DU WHY_DU DOSE-LIMITING TOXICITY FORM DLT_CYC OCC_CYC REL_ST	IF Trabectedin $((\text{Dose effectivement reçue VPRE_TRA and VOL_TRA/DOSE_TRA}) \leq 75\% \text{ AND INT_TRA} = 1 \text{ AND WHY_TRA} = 2 \text{ AND DLT_CYC} = 0)$ OR Durvalumab $((\text{Dose effectivement reçue VPRE_DU and VOL_DU / 1120 mg}) \leq 75\% \text{ AND INTER_D} = 1 \text{ AND WHY_DU} = 2 \text{ AND DLT_CYC} = 0)$ THEN TOL = 0
Patient goes off treatment over cycle 1 for reasons unrelated to toxicity (DLT or any other AE), e.g. progression, lost to follow-up	DISCONTINUATION VISIT END OF TREATMENT / end of treatment form DT_SOT DT_EOT EOTREASO DISCONTINUATION VISIT END OF TREATMENT / visit DIS_TRT TRA_EOT DUR_EOT DOSE-LIMITING TOXICITY FORM DLT_CYC AE FORM NUMAE AEVENT DT_AE MAX_INT TRA_MOD DUR_MOD	$\text{DT_EOT-DT_SOT} \leq 21 \text{ days}$ AND EOTREASO NOT IN (4 12) AND DLT_CYC=0 Additional control if $\text{DT_EOT-DT_SOT} \leq 21 \text{ days}$ 
 - Listing Other reason - Listing visit of end of treatment: DIS_TRT / TRA_EOT / DUR_EOT - Listing AE with TRA_MOD IN=3 OR DUR_MOD=3 THEN TOL=0
Population assessable for SAFETY	TOL (new variable)	TOL=1

2.4 Expansion cohort/ Evaluable for efficacy

- Population assessable for efficacy: All patients eligible and for whom the following conditions are satisfied:
 - Received at least one complete or two incomplete treatment cycles,
 - At least one disease measurement recorded not less than six weeks after treatment onset.
- The following patients will also be included in the population assessable for efficacy; they will be considered as “inevaluable for response” for the primary endpoint as per RECIST v1.1 criteria (i.e. objective response under treatment) and not be replaced in the primary efficacy analysis:
 - Any eligible patients who received at least one treatment cycle or two incomplete treatment cycles and experience disease progression or die due to disease progression prior to response evaluation (will be considered as “inevaluable for response” due to early, progression).
 - Patients withdrawn due to drug-related toxicity without any tumor assessments after the start of study treatment (will be considered as “inevaluable for response” due to toxicity).
 - Patients who received at least one administration of the treatment AND withdrawn due to significant clinical deterioration of unknown reason AND without any tumor assessments after the start of study treatment (will be considered as “inevaluable for response” due to significant clinical deterioration).
- Safety population: all patients having received at least one (any) treatment administration.

CREATION OF A NEW INDICATOR VARIABLE

New binary variable ELI_EFF

Label: « Evaluable for Efficacy »

ELI_EFF=1 if the patient is evaluable for the efficacy analysis

ELI_EFF=0 if the patient is not evaluable for the efficacy analysis

Criteria	eFORM variable	Control
Population evaluable for EFFICACY	ELI_EFF (new variable)	ELI_EFF = 1 IF

 Received one complete or two incomplete treatment cycles 	CYCLE 1 – DAY 1 AND DAY 2 (WEEK1) CYCLE 2 – DAY 1 AND DAY 2 (WEEK1) ADMI_TRA (1=Done) ADMI_DUR (1=Done) VPRE_TRA VOL_TRA VPRE_DUR VOL_DUR INT_TRA INTER_D	Cycle 1 completed $(C1_ADMI_TRA = 1 \text{ and } C1_ADMI_DUR = 1 \text{ and } (C1_VPRE_TRA = C1_VOL_TRA) \text{ and } (C1_VPRE_dur = C1_VOL_dur))$ Or Cycle 1 incomplete and Cycle 2 done $(C1_ADMI_TRA = 1 \text{ and } C1_ADMI_DUR = 1 \text{ and } ((C1_VPRE_TRA \neq C1_VOL_TRA) \text{ or } (C1_VPRE_dur \neq C1_VOL_dur))) \text{ and }$

		$((C2_ADMI_TRA = 1 \text{ or } C2_ADMI_DUR = 1) \text{ and } (C2_VOL_TRA > 0 \text{ or } C2_VOL_TRA > 0))$ Additional control: Date of start cycle Total dose given during cycle Therapy changes during cycle AND

 one disease measurement recorded not less than six weeks after treatment onset 	TUMOR ASSESSMENT (TUM_CYC) DIS_EVA (1=week 6) DT_MEAC	DIS_EVA =1 and Information on tumor assessment completed and date of tumor assessment OR IF
❖ Received at least one treatment cycle and experience disease progression or die due to disease progression prior to response evaluation after the start of study treatment	CYCLE 1 – DAY 1 AND DAY 2 (WEEK1) ADMI_TRA (1=Done) ADMI_DUR (1=Done) TREATMENT (EOTRT) EOTREASO (1=Disease progression and 12=Disease progression and Adverse event(s)) END OF STUDY (EOS) REA_STUD (3=Death) DT_DEATH CA_DEATH (1= Progression of disease) TUMOR ASSESSMENT (TUM_CYC) DT_MEAC (Date of measurement)	(C1_ADMI_TRA = 1 and C1_ADMI_DUR = 1) Additional control: Date of start cycle Total dose given during cycle Therapy changes during cycle AND $((EOTREASO \text{ in } (1 \text{ 12}) \text{ or } (CA_DEATH=1 \text{ and } EOS_REA = 3)) \text{ and } DT_MEAC \text{ is blank})$ OR IF
❖ withdrawn due to drug-related toxicity without any tumor assessments after the start of study treatment	DISCONTINUATION VISIT TRA_EOT (0=toxicity) DUR_EOT (0=toxicity) TUMOR ASSESSMENT (TUM_CYC) DT_MEAC (Date of measurement)	DT_MEAC is blank AND TRA_EOT =0 or DUR_EOT=0 OR IF
❖ Patients who received at least one administration of the treatment AND withdrawn due to significant clinical deterioration of unknown reason AND without any tumor assessments after the start of study treatment	TUMOR ASSESSMENT (TUM_CYC) DT_MEAC (Date of measurement) DISCONTINUATION VISIT END OF TREATMENT (EOTRT) DT_SOT, DT_EOT (start and end of treatment) EOTREASO (8= General or specific changes in patient's condition) ADVERSE EVENT FORM (AEV) DT_AE, DTENDAE (start and end date) TRA_MOD (3= Definitively stopped) DUR_MOD (3= Definitively stopped) TRA_REL (2= Unrelated) DUR_REL (2= Unrelated)	DT_MEAC is blank EOTREASO = 8

- Safety population: all patients having received at least one (any) treatment administration

CREATION OF A NEW INDICATOR VARIABLE

Patients will be evaluable for safety if they have received at least one treatment administration. (SAF=1).

New binary variable ELI_DLT

Label: « Safety population»

SAF=1 if the patient is assessable for safety

SAF=0 if the patient is not assessable for safety

Criteria	eFORM variable	Control
Safety population	CYCLE 1 – TREATMENT VOL_TRA (Administered volume) VOL_DUR (Administered volume)	SAF = 1 IF (VOL_TRA LE 0) AND (VOL_DUR LE 0) then SAF= 0

3 Statistical methods

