9.2.2. Phase I (Expansion cohorts)

- Eligible population: All patients included without major violation of eligibility criteria.

- Population assessable for efficacy: All patients eligible and for whom the following conditions are satisfied:
 - Received at least one complete or two incomplete treatment cycles,
 - At least one disease measurement recorded not less than six weeks after treatment onset.
- The following patients will also be included in the population assessable for efficacy; they will be considered as "inevaluable for response" for the primary endpoint as per RECIST v1.1 criteria (i.e. objective response under treatment) and not be replaced in the primary efficacy analysis:
 - Any eligible patients who received at least one treatment cycle or two incomplete treatment cycles and experience disease progression or die due to disease progression prior to response evaluation (will be considered as "inevaluable for response" due to early progression).
 - Patients withdrawn due to drug-related toxicity without any tumor assessments after the start of study treatment (will be considered as "inevaluable for response" due to toxicity).
 - Patients who received at least one administration of the treatment AND withdrawn due to significant clinical deterioration of unknown reason AND without any tumor assessments after the start of study treatment (will be considered as "inevaluable for response" due to significant clinical deterioration).
- Safety population: all patients having received at least one (any) treatment administration.

Patient's replacement:

- Any patient not eligible or not assessable for efficacy will be replaced.
- However, any patient who received at least one administration of the study drug will be included in the safety analysis.

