3.2.2 Expansion cohorts

- Analyses will be conducted separately for sarcoma and ovarian cancer patients.
- Primary efficacy endpoint will be analysed based on the eligible and assessable population:
 - Each patient will be assigned one of the following categories:
 - Complete response
 - Partial response
 - Stable disease
 - Progression
 - Inevaluable for response
 - The rate of objective response (complete or partial response) under treatment will be reported:
 - All eligible and assessable patients will be included in the denominator for the calculation of the objective response rate (ORR).
 - The 95% two-sided confidence limits will be provided for the ORR (binomial law).
 - First endpoint conclusions will be based on the objective response rate ORR for all eligible and assessable patients (section 10.2) after centralized radiological review of the data.
- As regards to the other efficacy endpoints, the analyses will be carried out in the eligible and assessable population:
 - Each patient will be assigned one of the following categories:
 - Complete response
 - Partial response
 - Stable disease
 - Progression
 - Inevaluable for response
 - The rate of best overall response will be calculated as the number of patients alive with the best response (recorded from the start of the treatment) divided by the number of patients eligible and assessable.
 - The 6-month progression-free rate will be calculated as the number of patients remaining alive and progression-free at 6 months from the start of the treatment divided by the number of patients eligible and assessable.
 - The 6-month objective response rate will be calculated as the number of patients alive with complete or partial response at 6 months divided by the number of patients eligible and assessable.
 - The 95% two-sided confidence limits will be provided for the calculated rates (binomial law)
- The safety analysis will be performed on the safety population.
- Quantitative variables will be described using mean and standard deviations if the normality assumption is satisfied, else other descriptive statistics (median, range, quartiles) will be reported.
- Qualitative variables will be described using frequency, percentage and 95% confidence interval (binomial law).
- Survival endpoints will be analysed using the Kaplan-Meier method. The median survival rates will be reported with a 95% confidence interval. Median follow-up will be calculated using the reverse Kaplan-Meier method.

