3.2.4 Secondary endpoints

For dose escalation part: Only the patients assessable for safety (TOL = 1) will take part into this analysis.

For expansion cohorts: Only the patients evaluable for efficacy (ELI_EFF = 1) will take part into this analysis.

Criteria	eFORM variable	Control
Objective response rate, defined as the rate of complete or partial response according to RECIST v1.1	
ASSE_CYC (TUMOR ASSESSMENT) DT_MEASC (date of measurement) ME1RTLC-ME5 RTLC (measures of lesions) SUM_RTLC (largest diameters) EVA1RLNMC-EVA5 RLNMC (non-measurable lesions eval) RES_RTLC, RES_RNTL (target and non-target lesions) OV_REV (overall response) CR=1, PR=2, SD=3, PD=4, NE=5 New variables : NB_BORR (nb of objective response case)
 
END OF STUDY (END_STU) DT_EOS (date of end of study)
	Status at each TUMOR ASSESSMENT
6-month objective response rate , defined as the rate of complete or partial response at 6 months according to RECIST v1.1	
ASSE_CYC (TUMOR ASSESSMENT) DT_MEASC (date of measurement) ME1RTLC-ME5 RTLC (measures of lesions) SUM_RTLC (largest diameters) EVA1RLNMC-EVA5 RLNMC (non-measurable lesions eval) RES_RTLC, RES_RNTL (target and non-target lesions) OV_REV (overall response) CR=1, PR=2 TREATMENT DT1_START ((Day 1 of treatment)) New variables : NB_ORR (nb of objective response case at 6months)
	DT_START filled in ME1RTLC-ME5 RTLC (filled in if needed) SUM_RTLC C filled in and check recist1.1 criteria EVA1RLNMC-EVA5 RLNMC (filled in if needed) RES_RTLC, RES_RNTL (filled in) Compute number of patients with OV_REV in (1 or 2) at 6 months
6-month Non-progression rate (NPR) defined as the percentage of patients with CR, PR or stable disease (SD) according to RECIST v1.1, (CR, PR or SD more than 24 weeks)	
ASSE_CYC (TUMOR ASSESSMENT) DT_MEASC (date of measurement) ME1RTLC-ME5 RTLC (measures of lesions) SUM_RTLC (largest diameters) EVA1RLNMC_EVA5RLNMC (non-
	DT_START filled in ME1RTLC-ME5 RTLC (filled in if needed) SUM_RTLC C filled in and check recist1.1 criteria EVA1RLNMC-EVA5 RLNMC (filled

	
measurable lesions eval) RES_RTL, RES_RNTL (target and non-target lesions) OV_RESP (overall response) CR=1, PR=2, SD=3 TREATMENT DT1_START ((Day 1 of treatment)) New variables : NB_NPR (nb of non-progression case at 6 months)
	
in if needed) RES_RTL, RES_RNTL (filled in) Compute number of patients with OV_REV in (1 2 3) at 6 month for at least 24 weeks

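### SAP 2.4 programs the exposure condition for the expansion efficacy population more narrowly than protocol 9.2.2, mainly by requiring both drugs in cycle 1

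*SAP*

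**What the plan says.** Protocol 9.2.2 sets the exposure condition as "Received at least one complete or two incomplete treatment cycles", together with a disease measurement at six weeks or later. SAP 2.1.2 and the opening of SAP 2.4 repeat it. No cycle number is named, and neither complete nor incomplete cycle is defined.

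The table in SAP 2.4 turns this into the flag ELI_EFF. Its exposure inputs are "CYCLE 1 – DAY 1 AND DAY 2 (WEEK1) CYCLE 2 – DAY 1 AND DAY 2 (WEEK1". Two branches are accepted:

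- Cycle 1 completed: C1_ADMI_TRA = 1, C1_ADMI_DUR = 1, and administered volume equal to prepared volume for both drugs.
- "Cycle 1 incomplete and Cycle 2 done": the same two flags equal to 1, a volume shortfall for at least one drug, either drug flagged as given in cycle 2, and the volume test "C2_VOL_TRA > 0 \text{ or } C2_VOL_TRA > 0".

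Three other routes lead to ELI_EFF = 1: early progression, toxicity and clinical deterioration. The toxicity row reads "DT_MEAC is blank AND TRA_EOT =0 or DUR_EOT=0".

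On the use of the flag, SAP 3.2.2 states "Primary efficacy endpoint will be analysed based on the eligible and assessable population", and protocol 9.3.2.2 agrees. SAP 2.1.2 adds "Any patient not eligible or not assessable for efficacy will be replaced". SAP 3.2.4 states "Only the patients evaluable for efficacy (ELI_EFF = 1) will take part into this analysis" for the secondary endpoints. SAP 3.2.3, however, heads the expansion primary-endpoint table with TOL=1, the flag built for the escalation part.

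**The concern.** The program and the written rule select different patients. Because both branches need both drugs in cycle 1, a patient who received trabectedin on day 1 but no durvalumab on day 2 of that cycle fails the exposure test, however many complete cycles follow. Because the cycle 2 volume test never reads durvalumab, a patient with an incomplete cycle 1 and durvalumab alone in cycle 2 also fails.

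The flag is the programmed form of the assessable population, so it fixes the ORR denominator and decides who is replaced. The go rule is at least one objective response among 14 assessable patients per cohort, so individual classifications matter.

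**Working it through.** **Plan's own figure.** Protocol 9.1 gives a 20% efficacy rate, 5% error, 14 assessable and 15 recruited per cohort. Gehan stage 1 takes the smallest n with (1 − 0.20)^n ≤ 0.05. Since 0.8^13 = 0.0550 and 0.8^14 = 0.0440, n = 14, as stated. With the 10% allowance, 15 × 0.9 = 13.5, so there is at most one spare patient. P(at least one response in 14) = 1 − (1 − p)^14, which is 95.6% at p = 20%, 77.1% at 10% and 51.2% at 5%.

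**Rule against program.** Let each drug in each cycle be not given, partly given or fully given: 3 × 3 = 9 states per cycle. With some drug given in cycle 1 (8 states) and anything in cycle 2 (9 states) there are 8 × 9 = 72 patterns. A one-drug cycle is taken as incomplete.

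| Cycle 1 | Cycle 1 states | Patterns meeting the protocol rule | Accepted by SAP 2.4 | Wrongly rejected |
|---|---|---|---|---|
| Both drugs, full volume | 1 | 1 × 9 = 9 | 9 | 0 |
| Both drugs, a shortfall | 3 | 3 × 8 = 24 | 3 × 6 = 18 | 6 |
| One drug only | 4 | 4 × 8 = 32 | 0 | 32 |
| Total | 8 | 65 | 27 | 38 |

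The other 72 − 65 = 7 patterns (incomplete cycle 1, nothing in cycle 2) fail both. The exposure clause accepts no pattern that fails the rule. These are counts of patterns, not of patients.

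**Which defect does the harm.** Correcting only the duplicated volume recovers 6 and leaves 32 rejected. Removing the both-drugs requirement and correcting the duplicate leaves 0, even if only cycles 1 and 2 are read. Over three cycles with none wholly skipped there are 584 patterns. Of these, 577 meet the rule and 235 are accepted, so 342 are rejected (288 for one drug in cycle 1, 54 for no trabectedin in cycle 2). Correcting the duplicate alone leaves 288; both corrections leave 0.

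**Sensitivity to the definition.** Suppose a one-drug cycle does not count as incomplete. The rule is then met by 9 + 3 × 4 + 4 × 1 = 25 of the two-cycle patterns. The program accepts 9 + 3 × 4 = 21 of them and rejects 4, all with one drug in cycle 1 and a complete cycle 2. It would also accept 3 × 2 = 6 patterns that fail the rule (trabectedin alone in cycle 2). The main defect survives; the duplicate then excludes nobody.

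**Effect on the decision (illustrations, since no frequency is given).**

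- One patient is 1/14 = 7.1 points. If the sole responder is dropped, 1/14 (exact 95% CI 0.2 to 33.9%) becomes 0/13 (0 to 24.7%), or 0/14 (0 to 23.2%) after a non-responding replacement. Go then becomes no-go with probability 1 − p: 80% at p = 20%, 95% at p = 5%.
- If k dropped and replaced patients all turn out to be non-responders, P(go) = 1 − (1 − p)^(14 + k). For k = 1, 2, 3 this is 96.5, 97.2 and 97.7% at p = 20% (from 95.6%), and 53.7, 56.0 and 58.2% at p = 5% (from 51.2%).
- If being dropped were unrelated to response, P(go) would stay at 1 − (1 − p)^14.

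**The case against.** Several limits on the point are fair.

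- **Failing the exposure clause is not the same as ELI_EFF = 0.** The flag has three other routes. The toxicity row has no brackets; if AND is evaluated before OR, any patient with DUR_EOT = 0 is admitted even with a scan. Some affected patients would be recovered that way, though by accident. The progression and clinical-deterioration routes need a blank measurement date, so they do not help a scanned patient.
- **A reader might infer that reading only cycles 1 and 2 excludes patients.** It does so only if a whole cycle is skipped. An incomplete cycle 1 with both drugs, followed by a complete cycle 2, passes.
- **A reader might infer that exclusion simply tracks poor tolerance.** Patients withdrawn for drug-related toxicity without a scan are expressly kept. What remains is a patient who misses a drug, stays on treatment and is scanned. With infusions on days 1 and 2 of one planned 24-hour stay, that group may be small.
- **A reader might infer that trabectedin alone in both cycles clearly meets the protocol rule.** It does not clearly do so, because an incomplete cycle is undefined. The SAP's own either-drug test for cycle 2 supports counting one-drug cycles, but only after both drugs were started in cycle 1.
- **The repeated variable may be a slip or a PDF-reading artefact.** VOL_DUR is among that row's inputs. The both-drugs finding does not depend on it.
- **The SAP lists additional controls on cycle dates, total dose and therapy changes.** These could reveal affected patients, but no rule lets them alter the flag.

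What stands against all of this is the patient with one drug in cycle 1, a later complete cycle and a scan. That patient meets the written rule under any definition of incomplete and fails the programmed exposure test.

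**Conclusion.** The exposure test in SAP 2.4 is wrong as written against protocol 9.2.2 and SAP 2.1.2. The both-drugs requirement in cycle 1 is the main defect; the duplicated trabectedin volume is secondary and should be checked against the source file. If a one-drug cycle counts as incomplete, 32 of the 38 wrongly rejected two-cycle patterns come from the first defect and 6 from the second. If it does not, the first defect remains in a smaller set.

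The loss from the primary ORR rests on SAP 3.2.2 and protocol 9.3.2.2 prevailing over the TOL=1 heading in SAP 3.2.3, and on no other route admitting the patient. The size is about 7 points of ORR per affected patient, with no basis in the documents for saying how many there would be. It would be too strong to say that one misclassified patient changes a cohort's conclusion: a go is lost only if that patient is the sole responder and the replacement does not respond. The point should be corrected before the first analysis, but it does not affect the sample size of 14.

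**What to change.** Replace the exposure control in SAP 2.4 with two counters over all cycles:

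- n_complete: cycles with ADMI_TRA = 1, ADMI_DUR = 1 and administered volume equal to prepared volume for both drugs.
- n_incomplete: other cycles with VOL_TRA > 0 or VOL_DUR > 0.
- Exposure is met if n_complete ≥ 1 or n_incomplete ≥ 2.

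State in the SAP that a one-drug cycle counts as incomplete, and settle explicitly whether a patient who never received durvalumab can be assessable. Use the same counters in the early-progression row: its text also allows two incomplete cycles, while its program requires both drugs in cycle 1. Correcting only the duplicated variable is not enough.

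For the flag to work as intended, also write the toxicity clause as DT_MEAC blank AND (TRA_EOT = 0 or DUR_EOT = 0), and replace TOL=1 above the expansion primary-endpoint table in SAP 3.2.3 with ELI=1 and ELI_EFF=1.

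The cost is a few lines of SAP program text, validated by the steering committee as protocol 9.3 already provides. It needs no new data and no protocol amendment, since it brings the program into line with the protocol text.
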